Protocol Non-CTIMP
Template Version 2.0 Review Date: December 2021

A cross-sectional study and a novel screening survey for radial artery assessment in surgical coronary revascularisation.

PROTOCOL

DATE 09/04/2024

CHIEF INVESTIGATOR – [name]

List Investigators – [name]
[name]
[name]

Investigation Sites: Royal Papworth Hospital; Royal Brompton Hospital

Principal Investigator: [name]

Protocol Identification Number: P00258

Date of Protocol: 20th November 2023

Review Date: 9th April 2024

Protocol Version Number: 4.0

Trial Sponsor: Royal Papworth Hospital (R&D Study Registration Number: P03105)

Contents

TRIAL OVERVIEW

1. Trial Overview	3
Primary Research Question	
Study Design	
Primary Outcome	
Secondary Outcome	
Rationale	
Schedule of Events	
2. Patient Recruitment	5
Study Population	
Inclusion Criteria	
Exclusion Criteria	
Recruitment Strategy	
3. Data Analysis and Document Retention	5
Sample Size	
Statistical Analysis	
4. Consent Process and Visit Schedule	6
Visit 1	
Follow-up Visit	
Informed Consent Procedure	
Table 1: Visit Schedule	
Table 2: Trial Specific Procedures versus Routine Procedures	
5. Follow up Visits and Travel Expenses	8
6. Data Collection and Auditing	9
Data Collection Form Completion	
Source Documentation	
Errors and Correcting	
Storage of Documents	
Retention of Documents	
Monitoring and Auditing	
7. Adverse and Serious Adverse Events	10
Recording & Reporting	
8. Amendments	11
Amendment log	

TRIAL OVERVIEW

1. Trial Overview

Primary Research Question

What factors influence the diagnostic accuracy of radial artery assessment in patients undergoing surgical coronary revascularisation?

Study Design

A multi-centre cross-sectional study to investigate the validity of radial artery assessment techniques in adults' people with ischaemic heart disease undergoing surgical coronary revascularisation with their radial artery being selected as an autologous graft conduit. Maximum expected duration of subject participation is 12 weeks.

Primary Outcome

Measure the sensitivity, specificity, negative and positive predictive values of the Modified Allen test (+/- pulse-oximetry), the Barbeau Test and ultrasonography examination.

Secondary Outcome(s)

- Measure the morphological and physiological quality of radial arteries through a validated structured questionnaire (Radial Artery Quality Evaluation Survey).
- Measure the patients' finger movements, cold tolerance sensitivity and tactile/touch perception through an ordinal symptoms scale (Follow-up Radial Artery Harvesting Scale).

Rationale

The study will explore the accuracy of radial artery (RA) assessment in people with ischaemic heart disease (IHD) undergoing coronary artery bypass grafting (CABG). IHD affects 2.3 million people in the United Kingdom and is responsible for over 65,000 deaths per year. CABG results in the most effective therapeutic strategy for multi-vessel IHD while the RA is one of the preferred graft conduits. A comprehensive peri-operative RA assessment is essential to ensure disease-free RA segments are selected, precluding surgical complications such as hand ischaemia and graft failure. Whilst numerous screening tests are documented, their validity (diagnostic accuracy) is under debate. The literature is lacking evidence regarding the use of a standardised protocol for RA screening. The patients' experiences are seldom considered while surgical complications still occur. The expert opinion of professionals involved within the RA assessment and harvesting, generally the surgical care practitioners (SCP), is also not explored.

The intended research will provide an in-depth understanding of how assessment techniques inform RA harvesting in patients undergoing CABG, calibrating clinical decision and improving surgical practice. The research will uplift the SCP profession and address knowledge gaps, resulting in disciplinary and academic contributions.

Schedule of Events

Patients taking part in the study will receive an assessment of the arterial forearm circulation from their non-dominant upper extremity through the observations below.

- **Pre-operative observations.** Before surgery (in the ward environment after the patient is being admitted or whilst patient in the anaesthetic room) the forearm blood circulation is measured through the measures 1, 2, 3 and 4 to inform decision to surgically expose the RA.

1) Modified Allen Test (MAT). Instruct the patient to clench his/her wrist while the examiner occlude with three fingers the patient's ulnar and radial arteries; instruct the patient to unclench his/her wrist; release the ulnar artery. The MAT result is negative or positive considering in how long the palm flushes:

≤5 seconds negative MAT; good collateral hand circulation (suggesting harvestable radial artery)
>5 seconds positive MAT; poor collateral hand circulation (suggesting not-harvestable radial artery)

2) Pulse-oximetry guided MAT. A pulse-oximetry probe is positioned on the patient's index finger; both radial and ulnar arteries are occluded by the examiner (with three fingers) until flattening of pulse waveform is obtained. Pressure on the ulnar artery is released and the result of the assessment is calculated considering in how long the pulse waveform returns to baseline:

≤5 seconds negative result (suggesting harvestable radial artery)
>5 seconds positive result (suggesting not harvestable radial artery)

3) Barbeau Test. A pulse-oximetry probe is positioned on the thumb; the radial artery is then compressed by the examiner, and the pulse waveform is analysed for up to 120 seconds, providing four patterns of ulnar-palmar patency:

- a. No damping of the pulse tracing immediately after compression (suggesting harvestable radial artery)
- b. Damping of the pulse tracing (suggesting harvestable radial artery)
- c. Loss of the pulse tracing, followed by recovery within 120 sec (suggesting harvestable radial artery)
- d. Loss of the pulse tracing, without recovery within 120 sec (suggesting not harvestable radial artery).

4) Ultrasonography examination of the forearm arteries. The radial artery is surgically exposed (negative result) when the following apply:

- a. ulnar artery inner diameter ≥2 mm
- b. radial artery inner diameter ≥2 mm
- c. absence of radial artery intraluminal calcifications and plaques.

- **Intra-operative observations.** The radial artery is surgically harvested when the following apply:

A) The radial artery morphological and physiological characteristics (diameter, calcifications, presence of pulsatile flow), quality of harvesting technique and surgical accessibility are considered satisfactory, good or optimal. Measures are taken through a structured questionnaire (Radial Artery Quality Evaluation Survey) currently being validated through a Delphi study.

B) Oxygen saturation reading (SpO_2) from the thumb through pulse-oximetry remains at 95% or above when an occlusive atraumatic clamp is applied on the mobilised RA.

- **Post-operative observations.** Patients' finger movements, cold tolerance sensitivity and tactile/touch perception is measured through an ordinal symptoms scale (Follow-up Radial Artery Harvesting Scale) at post-operative day 2-5 and at follow-up appointment (3-6 weeks after surgery). Bilateral comparison between hands and forearms will be undertaken. Tactile perception is assessed through Semmes-Weinstein monofilaments (single touch). Cold sensitivity is assessed through the use of ice-pack.

The Follow-up Radial Artery Harvesting Scale was developed from a verbal rating scale (VRS) questionnaire documented in the literature and considered an accurate rating method for pinpointing the intensity of cold sensation. The VRS questionnaire was re-adapted to appreciate people's post-operative experience with their finger movements, cold sensitivity and tactile/touch perception of their forearm and will be used in this cross-sectional study. A Patient and Public Involvement and Engagement (PPIE) was undertaken on the Follow-up Radial Artery Harvesting Scale, gaining feedback from 9 adult cardiac patients from a clinical institution from the Greater London region. The PPIE resulted in improving readability and clarity of the questions and answers included in the scale.

2. Patient Recruitment Criteria

Study Population

- Sixty-nine patients from two cardio-thoracic clinical institutions from the East of England and Greater London regions.
- Cardiovascular sample group.
- Recruitment period: April 2024 – February 2025.
- End of study: 31st March 2025.
The end of study is the date of the completion of any follow-up monitoring and data collection described in the protocol.

Inclusion

- Diagnosis of ischaemic heart disease / coronary artery disease
- Age \geq 18 years
- Male and Female participants
- Elective or urgent coronary artery bypass graft (CABG) surgery and radial artery (RA) harvesting, with the RA being selected as one of the autologous graft conduits for the coronary revascularisation.

Exclusion

- Paediatric patients
- Emergency CABG
- Patients lacking capacity to consent
- Patients with limited understanding of English language and non-English-speaking patients requiring use of interpreters

Recruitment

- The planned recruitment target rate is:
 - April – August 2024: 34 patients
 - September 2024 – February 2025: 35 patients
- The recruitment rate has been calculated based on evidence from retrospective data.
- *Recruitment review dates: June 2024, August 2024, November 2024, February 2024.*

Section 3. Sample Size and Data analysis

Sample Size

- A consecutive sampling method will be adopted for the recruitment of study participants. The minimum required number of participants to test and verify research hypotheses is sixty-nine patients (N=69). An adaptive trial design will be implemented: at quarterly assessment points the statistical power is assessed and the remaining sample size required is updated accordingly.

Statistical Analysis

- Sample size calculation was undertaken using G*Power software (version 3.1) using Chi-squared Test (χ^2) and adopting optimal effect size ($\omega=0.4$) and power (0.8).

4. Consent Process and Visit Schedule

Visit 1

- Potential participants will firstly be approached by clinicians within the healthcare team who is directly involved in delivering care and treatment to the patients. Clinicians will refer potential participants to the main investigator who will approach them for consenting purposes to take part in this study.

Follow-Up Visits

- Each patient will be assigned a study number; the study numbers will be allocated sequentially starting at 001.
- Visits should be scheduled and performed according to table 1.
- Trial specific procedures *versus* routine procedures are detailed in table 2 *if appropriate to the study*. The trial specific procedures will be performed after written informed consent has been obtained. The procedures that can be performed prior to consent being obtained are detailed in table 3 (*if appropriate*).

Table 1 Visit Schedule

Visit Number	Visit n	Visit n+1	Visit n+2
Time interval of Visit	week 0-3	week 0-3	week 4-12
Consent	X		
Pre-operative observation (Modified Allen Test +/- pulse-oximetry)		X	
Pre-operative observation (Barbeau Test)		X	
Pre-operative observation (Ultrasonography examination of forearm arteries)		X	
Intra-operative observation (oxygen saturation reading)		X	
Use of Questionnaire (Radial Artery Quality Evaluation Survey)		X	
Post-operative observation (Follow-up Radial Artery Harvesting Scale)			X

Table 2 Trial Specific Procedures *versus* Routine Procedures

Routine Investigations	Study Specific Procedures
Modified Allen Test +/- pulse-oximetry	Seeking Consent
Barbeau Test	Use of Questionnaire (Radial Artery Quality Evaluation Survey) currently under validation
Ultrasonography examination of forearm arteries	Use of Follow-up Radial Artery Harvesting Scale
Intra-operative oxygen saturation reading	

Informed Consent Procedure

- Patients will receive written and verbal information about the trial.
- Written informed consent will be obtained by a member of the trial team after a suitable time has elapsed during which the patient has had time to read the information sheet, consider the trial and ask any questions (Consent form). The Investigator must explain to each patient the nature

of the study, its purpose, the procedures involved, the expected duration, the potential risks and benefits involved and any discomfort it may entail (Ref. *International Conference of Harmonisation of Good Clinical Practice (ICH/GCP)5 4.8.7*

- The ultimate responsibility for obtaining written informed consent lies with the Investigator but this responsibility may be delegated to a suitably trained, and experienced person.
- Prior to the patient's participation in the study, the written informed consent form must be signed and personally dated by the patient and by the clinician who conducted the informed consent discussion (Ref. *ICH/GCP 4.8.8*). Each box at the end of each statement on the consent form must be signed by the patient.
- Each subject must be informed that participation in the study is voluntary and that he/she may withdraw from the study at any time and that withdrawal of consent will not affect his/her subsequent medical treatment (Ref. *ICH/GCP 4.8.10*).
- A copy of the informed consent document will be given to the patient (Ref. *ICH/GCP 4.8.11*). One copy will be filed in the patient's hospital case notes and a copy filed in the Trial Management File by the Clinical Research Nurses.
- The Clinical Research Nurse will ensure that the patient does not have any trial specific procedures prior to giving informed consent.
- If a patient withdraws their consent a line will be drawn diagonally through the consent form and labelled 'consent withdrawn' and signed and dated by a member of staff (please refer to Section 8 re labelling of case notes).

5. Follow-up Visits and Travel Expenses

Follow up Visits

The follow up visits will be in accordance with the visit schedule in table 1. The patients will be seen by the Researcher or Clinicians directly involved in the primary care for the patients for conducting the above presented observations. Clinicians directly involved in the patient care include Surgical Care Practitioners, Cardiothoracic Specialist Registrars and Advanced Nurse/Clinical Practitioners.

Travel Expenses

Participants are not required to travel to take part in the study as data will be collected during their hospital stay and during their pre- and/or post-operative follow up appointments to the clinical institutions.

6. Data Collection

Data Collection Form Completion

- The Investigator will ensure the accuracy, completeness, legibility and timeliness of the data recorded in the data collection forms (DCFs) and in all required reports to the Sponsor, R&D and REC.

Source Documentation

- The investigator must maintain source documents (patient's hospital case notes) for each patient in the study, consisting of all demographic and medical information, including laboratory data, and radiology results. A copy of the consent form and patient information sheet will also be filed in the patient's case notes. All information in the DCFs, apart from the questionnaires, must be traceable to and consistent with the source documents in the patient's hospital case notes (Ref. ICH/GCP 4.9.2).

Errors and Corrections

- Any change or correction to the DCF will be dated, initialled, and explained (if necessary) and should not obscure the original entry.

Storage of Documents

- DCFs will be kept in a locked filing cabinet or a locked room.

Retention of Documents

- All study documentation will be stored for 15 years after the last patient has completed their last visit.

Monitoring and Audit

- Upon request of the monitor, auditor, Sponsor, R&D, REC, MHRA or other regulatory authority, the Investigator will make available for direct access all requested study-related records.

The project data will be monitored by the Research Officer monthly. The first two patients from each participant site will be monitored in full. Thereafter fifty percent of the data will be monitored every month during the recruitment phase. After recruitment is complete ten percent of the data will be monitored.

7. Adverse and Serious Adverse Events

The definition of an adverse event is: 'Any untoward medical occurrence in a patient which does not necessarily have a causal relationship with this treatment'. This includes 'any unfavourable and unintended sign (including an abnormal laboratory finding), symptom or disease temporally associated with the study drug'. This may include, for example, a cold or an accident.

The definition of a serious adverse event is one that fulfils at least one of the following criteria:

- Is fatal- results in death
- Is life threatening
- Requires inpatient hospitalisation or prolongation of existing hospitalisation
- Results in persistent or significant disability/incapacity

OR

- Is a congenital anomaly/birth defect

Recording and Reporting

- No adverse and serious adverse events are predicted to occur for participants enrolling into this study.
- The chance of participants being identified from dissemination represents a risk of taking part in a research study. Every attempt will be made to avoid the identification of participants. Identity will be redacted from both participant information sheets and consent forms and no participants' details released to safeguard confidentiality.
- A general introduction to the research study (referral) will be made by someone else (NHS staff, acting as gatekeeper) to avoid pressuring participants best to participate.
- Agreement to participate in the study does not affect participant's legal rights.
- All research staff in contact with patients are responsible for noting adverse events that are reported by the patient and making them known to the Principal Investigator.
- At each visit or study assessment, adverse events that have occurred since the previous visit should be elicited from the patient. The event will be detailed in the patient's notes, as source document verification, including the start date (if known) and the end date.
- The action taken regarding the study procedure should be documented.
- Document any treatment/medication given for the event, including the dates the treatment/medication was commenced and the date it was stopped/changed, if applicable (an example of an AE form is in section 10 of the site file section). Documenting of adverse events is the responsibility of the Principal Investigator, Co-Investigator and Clinical Research Nurse/Assistant.
- Events, which are ongoing at the final study visit, should be followed up as clinically indicated.
- All serious adverse events (SAEs) will be documented as above using the appropriate reporting documentation in section 10 of the site file documents.
- All Unexpected SAEs should be reported to the hospital R&D department and may be require analysis through the hospital incident reporting system.
- Expected SAEs need to be reported to the Main REC in the annual REC report; the REC who performed the locality assessment does not need to be informed.
- Store all completed SAE forms with the patient's study documentation.

8. Amendments

Substantial amendments will be submitted to the Research Ethics Committee for review and approval.

Amendment Log

Revision	Section reviewed
1.	
2.	
3.

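### No reference standard is named for the primary accuracy outcome; if only scan-negative arteries are exposed and the reference is intra-operative, ultrasonography sensitivity, specificity and PPV cannot be estimated

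*Combined protocol and SAP*

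**What the plan says.** - **Primary Outcome (section 1):** "Measure the sensitivity, specificity, negative and positive predictive values of the Modified Allen test (+/- pulse-oximetry), the Barbeau Test and ultrasonography examination". Ultrasonography is therefore one of the tests under evaluation. No section says what its result is compared with.
- **Schedule of Events, pre-operative observations:** "the forearm blood circulation is measured through the measures 1, 2, 3 and 4 to inform decision to surgically expose the RA".
- **Schedule of Events, measure 4 (ultrasonography):** "The radial artery is surgically exposed (negative result) when the following apply", followed by three scan criteria. The other three tests are only said to suggest whether the artery is harvestable.
- **Schedule of Events, intra-operative observations:** the artery is harvested when A and B apply. A is a survey of artery quality that also asks whether "quality of harvesting technique and surgical accessibility are considered satisfactory, good or optimal". B is a thumb oxygen saturation threshold "when an occlusive atraumatic clamp is applied on the mobilised RA".
- **Inclusion (section 2):** CABG surgery and "radial artery (RA) harvesting, with the RA being selected as one of the autologous graft conduits".
- **Table 1 (section 4):** the row "Intra-operative observation (oxygen saturation reading") and the survey row are marked at the second visit with no exception for arteries that are not exposed.
- **Statistical Analysis (section 3):** one sentence on the sample size calculation. It contains no analysis of the accuracy measures and nothing on unverified patients.

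**The concern.** An accuracy study needs the true status of arteries that test positive as well as those that test negative. Here the result of a test under evaluation helps to decide whether the artery is exposed, and the only observations that look like a reference standard require exposure. If a positive scan always means no exposure, half of the ultrasonography two-by-two table is empty by design. A report computed on verified arteries would then show perfect specificity whatever the scan's real performance. Counting unexposed arteries as not harvestable would be no better, because the scan would become its own reference.

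The study is meant to inform how arteries are chosen for harvest, so an artefact of this kind in the primary outcome would matter.

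**Working it through.** **The plan's own figure.** The only figure is N = 69 (section 3: chi-squared test, effect size 0.4, power 0.8). With noncentrality 69 × 0.4² = 11.04, power is 0.8055 at alpha 0.05 and 3 degrees of freedom, and 69 is the smallest N that reaches 0.8 there. Alpha and degrees of freedom are assumptions, since the plan states neither. This figure has no bearing on empty cells.

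**Step 1: the table if only scan-negative arteries are verified.** In the plan's labelling, positive means not harvestable. Verified true positives (TP) and false positives (FP) are both 0. With FN false negatives and TN true negatives:
- sensitivity = 0/(0 + FN) = 0%, or 0/0 if FN = 0
- specificity = TN/(TN + 0) = 100%
- PPV = 0/0
- NPV = TN/(TN + FN), which can be estimated

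No sample size changes this. Reweighting does not help either, because the probability of verification after a positive scan is zero.

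**Step 2: an illustration with 69 patients.** The documents give no prevalence or accuracy. Assume 15% not harvestable, scan sensitivity 80% and specificity 90%.
- FN = 69 × 0.15 × 0.20 = 2.07
- TN = 69 × 0.85 × 0.90 = 52.79
- exposed = 2.07 + 52.79 = 54.86; unexposed = 69 − 54.86 = 14.14

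Rounded to FN 2, TN 53 and 14 unexposed:

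| Measure | Computed on verified arteries | Worst-case bounds using the 14 unexposed |
|---|---|---|
| Sensitivity | 0/2 (exact 95% CI 0–84.2%) | 0 to 14/16 = 87.5% |
| Specificity | 53/53 = 100% (93.3–100%) | 53/67 = 79.1% to 100% |
| PPV | 0/0 | 0 to 100% |
| NPV | 53/55 = 96.4% (87.5–99.6%) | not needed |

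The specificity interval excludes the 90% that was assumed true. With 2.07/54.86 = 3.8% not harvestable among 55 exposed, the chance of no false negatives at all is (1 − 0.038)^55, about 12%; sensitivity is then 0/0. With unrounded counts, the upper bound for sensitivity and the lower bound for specificity are 89.5% and 82.7% at prevalence 10%, and 83.8% and 67.0% at 30%.

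**Step 3: if a share q of scan-positive arteries is exposed, unrelated to harvestability.** Uncorrected sensitivity = 0.8q/(0.8q + 0.2); uncorrected specificity = 0.9/(0.9 + 0.1q).

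| q | Sensitivity (true 80%) | Specificity (true 90%) |
|---|---|---|
| 10% | 0.08/0.28 = 29% | 0.90/0.91 = 98.9% |
| 25% | 0.20/0.40 = 50% | 0.90/0.925 = 97.3% |
| 50% | 0.40/0.60 = 67% | 0.90/0.95 = 94.7% |

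**Step 4: the other three tests.** With an intra-operative reference, their measures also come only from exposed arteries. Assume a Modified Allen Test with sensitivity 70% and specificity 85%, and errors independent of the scan's given true status. NPV in all patients is 0.7225/(0.7225 + 0.045) = 94.1%. Among exposed arteries, with 3.8% not harvestable, it is 0.818/(0.818 + 0.0113) = 98.6%. Other dependence structures give other values, so this shows only that the two quantities can differ.

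**Step 5: the inclusion criterion.** If it means completed harvest, and harvest follows rule A and B, every participant has met both. Every participant is then reference-negative, and NPV is also fixed at 100%.

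**The case against.** The strongest reply is that the empty cells need two premises that the protocol does not state. The ultrasonography sentence says *when*, not *only when*. All four tests are said to inform exposure, so a scan-positive artery might still be exposed. Table 1 schedules the intra-operative observations for everyone. This stands: a reader might infer that scan-positive arteries are never exposed and that the three measures are certainly lost, but the text conflicts on the first part, so the second is conditional. It does not remove the problem. Incomplete verification biases the measures (step 3), and no correction is planned. Only complete verification would avoid both, and no passage says that it will occur.

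Other inferences also go further than the documents:
- **That sensitivity is always 0%.** It is 0/0 when no false negative occurs.
- **That not harvestable has no definition.** The protocol gives a harvest rule, A and B. What is missing is a statement that this rule is the reference standard, and whether the technique and accessibility items in A count, since they do not describe the artery itself.
- **That patients are tested before enrolment, so that scan-positive patients never enter.** Table 2 lists the tests as routine, and "The trial specific procedures will be performed after written informed consent has been obtained" covers only trial-specific procedures. But the Schedule of Events describes tests on patients already taking part, and Table 1 puts consent a visit earlier. The procedures allowed before consent are left to a Table 3 that is marked as optional and does not appear. This reading is possible but less likely.
- **That the post-operative scale could be the reference.** It is a secondary outcome that records hand and forearm symptoms after harvesting. It does not clearly show whether an unexposed artery was harvestable.

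**Conclusion.** The concern holds in conditional form and should be fixed before any accuracy result is produced. One gap does not depend on interpretation: no reference standard is named for the primary outcome. On the natural reading of the Schedule of Events (exposure only after a negative scan, intra-operative reference), three of the four primary ultrasonography measures are fixed or undefined by design and only NPV among exposed arteries remains. If some scan-positive arteries are exposed, all four can be computed, but uncorrected sensitivity is too low and specificity too high under the assumptions of step 3. If inclusion means completed harvest, which is the less likely meaning, NPV is lost as well.

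The algebra in step 1 needs no assumed figures. All percentages in steps 2 to 4 rest on assumed prevalence and accuracy, and the conclusion does not depend on them.

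**What to change.** None of these changes alters the clinical rule or adds a procedure.

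1. **Name the reference standard.** If it is the harvest rule (A and B), state whether the technique and accessibility items of A count towards not harvestable.
2. **Reconcile the Schedule of Events, the inclusion criteria and Table 1.** State whether scan-positive arteries are ever exposed, whether unexposed patients stay in the study, and, if this is what is intended, that eligibility means planned and not completed harvest.
3. **Match the ultrasonography outcome to the answer.**
   - If scan-positive arteries are not verified, restate it as NPV among exposed arteries with an exact 95% CI. Give no point estimate of sensitivity, specificity or PPV. Worst-case bounds may be given if unexposed patients stay enrolled.
   - If some are verified, report verified counts by scan result and apply a partial-verification correction such as Begg-Greenes. State its assumption that, given the test result, verification is unrelated to true status.
4. **If the reference is intra-operative,** label the measures for the Modified Allen Test, its pulse-oximetry version and the Barbeau Test as conditional on exposure. Report the number unexposed by each test result.

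The cost is a narrower headline: ultrasonography NPV plus exposure-conditional estimates in place of full diagnostic accuracy. Intervals will be wide (in the illustration, NPV 96.4% with exact 95% CI 87.5–99.6%). A partial-verification correction would rest on few arteries: about 4 if 25% of the 14 scan-positive arteries were exposed (14 × 0.25 = 3.5).

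### Three bedside tests of collateral flow carry a harvestability label; if the harvest verdict is the reference, failures on radial morphology, technique or access alone count as their false negatives

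*Combined protocol and SAP*

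**What the plan says.** The primary outcome (section 1) is to "Measure the sensitivity, specificity, negative and positive predictive values of the Modified Allen test (+/- pulse-oximetry), the Barbeau Test and ultrasonography examination". It states no target condition for any test and names no reference standard. The Statistical Analysis part of section 3 holds only sample size inputs.

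The Schedule of Events in section 1 then describes each observation:

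- **Modified Allen Test.** A fast flush is read as "good collateral hand circulation (suggesting harvestable radial artery" and a slow one as "poor collateral hand circulation (suggesting not-harvestable radial artery".
- **Oximetry-guided Allen test.** It times the return of the pulse waveform once the ulnar artery is released. It carries the same two labels.
- **Barbeau test.** The radial artery is compressed and the tracing is classified, "providing four patterns of ulnar-palmar patency". Three patterns are labelled harvestable and one not.
- **Ultrasound.** "The radial artery is surgically exposed (negative result) when the following apply": an ulnar diameter criterion (4a), a radial diameter criterion (4b), and "absence of radial artery intraluminal calcifications and plaques" (4c). This result is tied to exposure, not to the word harvestable.
- **Intra-operative verdict.** The artery is harvested when two conditions apply. Part A is that "The radial artery morphological and physiological characteristics (diameter, calcifications, presence of pulsatile flow), quality of harvesting technique and surgical accessibility are considered satisfactory" or better. Part B is that thumb oxygen saturation "remains at 95% or above when an occlusive atraumatic clamp is applied on the mobilised RA".

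Table 1 lists the intra-operative saturation reading and the quality survey on separate rows.

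**The concern.** The three bedside tests ask whether the hand would stay perfused without the radial artery. None of them looks at the radial wall or lumen, and none can foresee harvesting technique or surgical access. Their labels nevertheless point to harvestability, and the only definition of a harvested artery includes all of those things.

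If accuracy is judged against that definition, a test can be right about collateral flow and still be counted wrong. A low published sensitivity could then be taken as poor performance of the test when it reflects a different target condition. The rationale names two complications, hand ischaemia and graft failure. A single pooled verdict does not show which of the two a technique helps to foresee.

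Naming A and B together as the reference would not cure this. The mismatch is therefore a separate matter from the missing reference standard.

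**Working it through.** **The plan's own figure.** Section 3 gives N = 69 from a chi-squared test with effect size 0.4 and power 0.8. Alpha and degrees of freedom are not stated. With noncentrality N × 0.4² and alpha 0.05 (assumed), the smallest N is 50 for 1 df, 61 for 2 df, 69 for 3 df (power 0.8055) and 75 for 4 df. So 69 reproduces with alpha 0.05 and 3 df. The point below does not depend on this; 69 is used only to turn rates into counts.

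**Which observation covers which condition**

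| Observation | Collateral supply | Radial diameter or calcification | Technique, access |
|---|---|---|---|
| Allen, oximetry-guided Allen, Barbeau | yes | no | no |
| Ultrasound | 4a (ulnar diameter) | 4b, 4c | no |
| Part A | no | yes | yes |
| Part B | yes (saturation with the radial artery clamped) | no | no |

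**Effect of using A and B as the reference.** Positive means not harvestable. Let c be the rate of collateral failure, assumed to be what B detects, and m the rate of failure on A. The documents give neither rate, so both are assumed, and they are taken as independent. Consider a test that is perfect for collateral failure, with every patient verified:

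- Not harvestable = 1 − (1 − c)(1 − m)
- Sensitivity = c / [1 − (1 − c)(1 − m)]
- NPV = (1 − c)(1 − m) / (1 − c) = 1 − m
- Specificity = PPV = 1, because every collateral failure is also not harvestable

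| c | m | Not harvestable | Sensitivity | NPV | False negatives / not harvestable, of 69 |
|---|---|---|---|---|---|
| 5% | 5% | 0.0975 | 0.51 | 0.95 | 3.3 / 6.7 |
| 5% | 10% | 0.145 | 0.34 | 0.90 | 6.6 / 10.0 |
| 10% | 10% | 0.19 | 0.53 | 0.90 | 6.2 / 13.1 |
| 10% | 20% | 0.28 | 0.36 | 0.80 | 12.4 / 19.3 |

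For the second row: 1 − 0.95 × 0.90 = 0.145, and 0.05 / 0.145 = 0.34. Over c = 2–15% and m = 2–20%, sensitivity runs from 0.90 down to 0.09. At m = 0 (a pure collateral reference) it is 1.00.

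**An imperfect test.** Take 90% sensitivity and 90% specificity for collateral failure, with c = 5% and m = 10%. True positives are 0.9 × 0.05 + 0.1 × 0.95 × 0.10 = 0.0545, so apparent sensitivity is 0.0545 / 0.145 = 0.38. Specificity stays at 0.90.

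Equivalently, if f is the share of non-harvestable arteries that fail on A alone, apparent sensitivity is 0.9(1 − f) + 0.1f. This gives 0.66, 0.50 and 0.34 at f = 0.3, 0.5 and 0.7 (assumed values). The case just worked has f = 0.095 / 0.145 = 0.66.

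**Who receives a verdict.** A and B are intra-operative, and B needs a mobilised artery under clamp. The only explicit exposure rule is ultrasound 4a–4c. Arteries positive on ultrasound are therefore by rule not exposed and have no A or B result. This removes many morphology failures from the verified group, so m there may be below the values above.

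**The case against.** The strongest objection is that no passage scores any test. A reader might infer that the protocol already counts sound collateral tests as failures. It does not say so: the harvest rule states when an artery is taken, not how accuracy is judged. That stands, and the point is conditional on the harvest verdict becoming the reference.

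A reader might also infer that ultrasound is favoured because it covers both conditions. The documents do not support that. If the exposure rule is followed, every verified artery is ultrasound-negative, so each failure on A or B is an ultrasound miss and its apparent sensitivity among verified patients is zero. If unexposed arteries were instead counted as not harvestable, ultrasound would be favoured by construction. The protocol does not say which applies.

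For the same reason, an artery whose calcification is seen on ultrasound is not a fair illustration. It fails 4c, is not exposed, and cannot fail A.

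Nor is it right that the study could never separate the two problems. Saturation and survey are recorded separately, so for exposed patients the data can be split.

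Finally, all four measures inform one exposure decision, and accuracy for that overall decision is a legitimate pragmatic question. It deserves its own label. It is not a measure of how well a collateral test detects poor collateral flow.

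**Conclusion.** The mismatch is in the text; its numerical effect is conditional. If the verdict combining A and B serves as the reference, failures on A alone become false negatives of the three bedside tests. Their sensitivity and NPV fall, while specificity and PPV are not lowered.

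The loss of sensitivity can be large: about 0.34 for a perfect collateral test at 5% collateral failure and 10% failure on A. The loss of NPV is smaller, to 0.90 in the same case. These figures rest on assumed independent rates, on B capturing collateral failure, and on full verification. The true size is unknown and may be smaller, because the ultrasound criteria screen who is exposed. No direction of bias can be claimed for ultrasound.

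**What to change.** Before analysis, amend the primary outcome and analysis text as follows:

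1. Score the Modified Allen Test, the oximetry-guided Allen test and the Barbeau test (and ultrasound criterion 4a where verified) against observation B, among patients whose artery is mobilised and clamped.
2. Report accuracy against the combined A and B verdict as a separate, labelled analysis of each technique's overall yield.
3. Record which of 4a, 4b, 4c, A and B failed, not only the overall result.
4. Compare 4b and 4c with the survey's diameter and calcification items descriptively only, and state that unexposed arteries are unverified. The survey is not in the documents, so confirm that these items can be read separately.

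The change needs revised wording and component-level recording on the data collection forms, but no new procedure. The price is precision. With all 69 verified, 5% collateral failure gives about 3.5 positives for B (69 × 0.05), against 10.0 for the combined verdict when 10% fail on A. Even 3 detected out of 3 leaves an exact 95% lower limit of 0.025^(1/3) = 0.29 for sensitivity. Partial verification is not solved: patients who are never exposed have neither A nor B, and if positive bedside results also deter exposure, sensitivity against B is affected too. The report should say so.
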